### **11.3. Adverse Events of Special Interest**

Adverse events of special interest (AESI) are pruritus, hepatic disorders, dyslipidaemia, and myopathy. For each of these AESI, subject incidence of TEAEs and the total number of entries by MedDRA system organ class and preferred term will be presented. In addition, for each AESI, the time to first onset and time to most severe event will be summarized using descriptive statistics.

- Time to first onset of AESI event
  - The time to the onset of the first event will be calculated by date of onset of first event – date of first dose of investigational product + 1.
  - Subjects without AESI events will be censored at the date of completion or early termination.

- Time to start of most severe of AESI event
  - The time to the onset of the most severe event will be calculated by date of onset of most severe event – date of first dose of investigational product + 1.
  - Subjects without AESI events will be censored at the date of study completion or early termination.

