### **11.3.1. Pruritus**

Treatment-emergent pruritus, defined as any preferred term that contains “*Prur*,” will be summarized separately by the MedDRA SOC, treatment group, and PT as a subset of all TEAEs.

An analysis of treatment-emergent pruritus event days per subject years on study will be performed. The days at each severity grade, including the total days of event, and the percent of event days on study at each severity grade, including the total, will be summarized.

In order to explore the relationship between pruritus and the investigational product, the following time-to-event analyses will be performed:

- Total duration of treatment-emergent pruritus
  - Duration of each treatment-emergent pruritus event will be calculated as end date – start date +1. For events that are ongoing at Week 16, the Week 16 date will be used as the end date. The sum of each event will be summed for an overall by-patient duration during the DB phase.
- Time to first onset of treatment-emergent pruritus
  - The time to the start of the first episode will be calculated by date of onset of first episode – date of first dose of investigational product + 1.
  - Subjects who never report an AE of pruritus will be censored at the date of completion or discontinuation.
- Time to onset of the most severe treatment-emergent pruritus
  - The time to the start of the most severe pruritus will be calculated by date of onset of the most severe pruritus – date of first dose of investigational product + 1.
  - Subjects who never report a severe AE of pruritus will be censored at the date of study completion or discontinuation.
- Time to resolution of the most severe treatment-emergent pruritus event
  - The time to resolution of the most severe event of treatment-emergent pruritus will be calculated by date of resolution of the most severe event of treatment-emergent pruritus – start date of the most severe event of treatment-emergent pruritus + 1.
  - Subjects whose most severe event of treatment-emergent pruritus is ongoing will be censored at the date of study completion or discontinuation. For subjects that are lost to follow-up, the last contact date will be used.
  - Only subjects that report a pruritus event are included in this analysis.

- For subjects reporting multiple events at the most severe level, the event with the longest duration will be used.
- Separate summaries will be presented for those who discontinue due to pruritus.

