## **11.4. Adjudicated Cardiovascular Events**

All suspected cardiovascular events that occur after administration of the first dose of investigational product will be reviewed and adjudicated by the Cardiovascular Adjudication Committee according to criteria defined in their charter. Events adjudicated by the committee will be included in the cardiovascular event analysis.

Summaries that are displayed by system organ class and preferred terms will be ordered by descending order of incidence, for all OCA-treated patients, of system organ class and by preferred terms within each system organ class. All summaries of incidence will include the associated exact binomial 95% CI. Summaries of the following types will be presented by treatment group:

- Subject incidence of adjudicated cardiovascular events and the total number of entries by MedDRA system organ class and preferred term

In order to explore the relationship between adjudicated cardiovascular events and the investigational product, the following time-to-event analyses will be performed:

- Time to first onset of adjudicated cardiovascular event

- The time to the start of the first event will be calculated by date of onset of first event – date of first dose of investigational product + 1.
- Subjects without adjudicated events will be censored at the date of completion or early termination.
- Time to onset of most severe adjudicated cardiovascular event
  - The time to the onset of most severe event will be calculated by date of onset of most severe event – date of first dose of investigational product + 1.
  - Subjects without adjudicated events will be censored at the date of completion or early termination.

The incidence and time-to-event analysis for adjudicated cardiovascular events will be repeated for suspected cardiovascular events.

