14.3.1.13.1	Safety	Summary of Pre-Treatment Serious Adverse Events by System Organ Class and Preferred Term
14.3.1.13.2	Safety	Summary of Pre-Treatment Serious Adverse Events by Preferred Term
14.3.1.14.1	Safety	Summary of Pruritus Treatment-Emergent Adverse Events by System Organ Class and Preferred Term

Table Number	Population	Table Title
14.3.1.14.2	Safety	Summary of Pruritus Treatment-Emergent Adverse Events by Preferred Term
14.3.1.14.3	Safety	Time to Onset of First Treatment-Emergent Pruritus
14.3.1.14.4	Safety	Time to Onset of Most Severe Treatment-Emergent Pruritus
14.3.1.14.5	Safety	Time to Resolution of Most Severe Treatment-Emergent Pruritus
14.3.1.14.6	Safety	Treatment-Emergent Pruritus Event Days
14.3.1.15.1	Safety	Summary of Treatment-Emergent Hepatic Disorder Adverse Events by System Organ Class and Preferred Term
14.3.1.15.2	Safety	Summary of Treatment-Emergent Hepatic Disorder Adverse Events by Preferred Term
14.3.1.15.3	Safety	Time to Onset of First Treatment-Emergent Hepatic Disorder
14.3.1.15.4	Safety	Time to Onset of Most Severe Treatment-Emergent Hepatic Disorder
14.3.1.16.1	Safety	Summary of Treatment-Emergent Dyslipidaemia Adverse Events by System Organ Class and Preferred Term
14.3.1.16.2	Safety	Summary of Treatment-Emergent Dyslipidaemia Adverse Events by Preferred Term
14.3.1.16.3	Safety	Time to Onset of First Treatment-Emergent Dyslipidaemia
14.3.1.16.4	Safety	Time to Onset of Most Severe Treatment-Emergent Dyslipidaemia
14.3.1.17.1	Safety	Summary of Treatment-Emergent Myopathy Adverse Events by System Organ Class and Preferred Term
14.3.1.17.2	Safety	Summary of Treatment-Emergent Myopathy Adverse Events by Preferred Term
14.3.1.17.3	Safety	Time to Onset of First Treatment-Emergent Myopathy
14.3.1.17.4	Safety	Time to Onset of Most Severe Treatment-Emergent Myopathy
14.3.1.18.1	Safety	Summary of Treatment-Emergent Adjudicated Cardiovascular Treatment-Emergent Adverse Events by System Organ Class and Preferred Term
14.3.1.18.2	Safety	Summary of Treatment-Emergent Suspected Cardiovascular Treatment-Emergent Adverse Events by System Organ Class and Preferred Term
14.3.1.18.3	Safety	Time to Onset of First Treatment-Emergent Adjudicated Cardiovascular Event
14.3.1.18.4	Safety	Time to Onset of First Treatment-Emergent Suspected Cardiovascular Event
14.3.4		Clinical Laboratory Evaluations
14.3.4.1.1	Safety	Summary of Hematology and Coagulation – SI Units
14.3.4.1.2	Safety	Summary of Hematology and Coagulation – CV Units

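### Time to most severe event in Sections 11.3 and 11.4 has no fixed grade, so it does not compare severity between arms and lengthens when a subject's events escalate

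*SAP*

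**What the plan says.** Section 11.3 of the SAP covers the adverse events of special interest (AESIs). It states that "for each AESI, the time to first onset and time to most severe event will be summarized using descriptive statistics". The severity variable is then defined: "The time to the onset of the most severe event will be calculated by date of onset of most severe event", minus the date of first dose, plus 1. Its censoring rule is "Subjects without AESI events will be censored at the date of study completion or early termination". No grade appears in either line.

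Section 11.4 uses the same construction for adjudicated cardiovascular events, and repeats it for suspected ones: "The time to the onset of most severe event will be calculated by date of onset of most severe event". Its censoring rule is "Subjects without adjudicated events will be censored at the date of completion or early termination". The stated purpose is explanatory: "In order to explore the relationship between adjudicated cardiovascular events and the investigational product, the following time-to-event analyses will be performed".

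Section 11.3.1, on pruritus, censors by grade instead: "Subjects who never report a severe AE of pruritus will be censored at the date of study completion or discontinuation".

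Appendix A lists outputs for the variable. Table 14.3.1.15.4 is "Time to Onset of Most Severe Treatment-Emergent Hepatic Disorder", and 14.3.1.16.4 and 14.3.1.17.4 are its dyslipidaemia and myopathy counterparts. For cardiovascular events Appendix A lists only the first-onset tables, 14.3.1.18.3 and 14.3.1.18.4.

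**The concern.** A reader will take a table of time to the most severe hepatic or muscle event as information on how soon serious trouble starts in each arm. The definition does not give that. Each subject is measured against their own worst episode, so a subject whose worst event is mild and one whose worst event is severe both count as having the event. Which record counts is known only once follow-up has ended.

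The date moves in the wrong direction. Where a mild event is followed by a worse one, the subject's time becomes longer, so worsening on treatment reads as later onset. Atorvastatin is added at Week 4 (Section 4), so worsening after an early mild event is a pattern that a reader might well look for in these tables.

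**Working it through.** The plan gives no figure on this point, so there is nothing to reproduce. The definition can be applied directly.

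**Step 1: what follows from the definition.** For a subject with at least one event, let F be the onset of the first event and W the onset of the worst, both counted from first dose plus 1.

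- The event indicator is the same for F and W, because only subjects with no event are censored.
- W is never less than F. With ties in grade resolved to the earliest event (an assumption, since Sections 11.3 and 11.4 give no tie rule), W exceeds F only if a later event has a higher grade.
- Grade enters only within a subject. A single mild event on Day 10 and a single severe event on Day 10 both give W = 10.

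**Step 2: worked case.** A placebo subject has one mild event on Day 10, so W = 10. A subject on obeticholic acid (OCA) has a mild event on Day 10 and a severe one on Day 80, so W = 80. Both count as events. The worse course is 80 − 10 = 70 days later.

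**Step 3: size under assumed inputs.** From the SAP: 20 subjects per group (Section 5) and 16 weeks, or 112 days (Section 4). Assumed: first event uniform on Days 1 to 56 in both arms; control events never escalate; the stated share of active-arm subjects with an event escalates 14 to 56 days later; all severe events arise by escalation. There were 1,500 trials per row. Medians are among subjects with an event, averaged over trials. Z is the mean log-rank statistic; positive means the active arm is worse.

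| Incidence, control / active | Active subjects with an event who escalate | Median W, control / active (days) | Z, first onset | Z, own worst event | Z, first severe event |
|---|---|---|---|---|---|
| 50% / 50% | 50% | 28.4 / 44.9 | −0.02 | −0.35 | +2.34 |
| 50% / 50% | 100% | 28.0 / 63.7 | −0.01 | −0.66 | +3.66 |
| 30% / 30% | 50% | 28.5 / 44.4 | −0.03 | −0.16 | +1.66 |
| 30% / 30% | 100% | 28.1 / 64.1 | 0.00 | −0.24 | +2.61 |
| 10% / 10% | 50% | 28.1 / 46.1 | 0.00 | −0.02 | +0.78 |
| 30% / 50% | 50% | 28.6 / 44.6 | +1.29 | +1.09 | +2.33 |

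The later median appears in every row. The log-rank columns show direction only, because the plan writes no such test for these events. In the last row incidence is higher on active treatment. A log-rank test would then still point to harm, but the descriptive median is again later.

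**Step 4: dependence on the assumptions.** A second set-up used exponential first onset, an exponential lag to escalation with mean 35 days, and 5% of events severe at first onset in both arms.

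- 50% first-onset risk, with 80% of OCA events and no placebo events escalating: median W is about 65 days on OCA and 48 on placebo. A log-rank test shows harm in 1.7% and benefit in 4.2% of trials on W, and harm in 76% on time to first severe event.
- 20% risk, with 30% and 10% escalating: medians are 59 and 55 days, and time to first severe event shows harm in only 1.2%.
- 10% risk, with 80% and 0% escalating: 2.3% on time to first severe event. At 20% risk with the same escalation it is 17.5%.
- 50% risk, with 30% and 10% escalating: 8.8% on time to first severe event.

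The direction comes from the definition. The size comes from inputs that the SAP does not contain.

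**The case against.** A reader might infer that the plan cannot distinguish a drug that turns mild events into severe ones. The document does not support that. Section 11.2 plans subject incidence by maximum severity for all treatment-emergent events, by treatment group (Tables 14.3.1.11.1 and .2), and repeats it for events up to Week 4 (14.3.1.11.3 and .4). Comparing the two periods shows coarsely whether severity rises later. Serious-event summaries, summaries of events leading to withdrawal, and a listing of severe events (16.2.7.3) are also planned. These objections stand, and they limit the point to one variable.

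A reader might also infer that a formal comparison would declare the escalating arm safer. The AESI times are summarised descriptively. Kaplan-Meier and log-rank methods are written only under pruritus, Section 11.4 names no test, and Section 6.2.8 makes every p-value descriptive. Even if a log-rank test were run, 4.2% apparent benefit against a nominal 2.5% per side is close to no signal.

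Three further objections stand in part:

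- The lengthening needs the worse episode to be a separate record with its own onset date. If one record carries the highest grade reached, W equals F and nothing is distorted, but the variable then adds nothing to first onset. The SAP does not state the recording rule, and the protocol or case report form guidance may.
- The cardiovascular variable has no table in Appendix A, so in Section 11.4 only the text is affected.
- When a subject's worst episode began is a legitimate descriptive question. It is not a comparison of severity between arms, though, and the table titles invite that reading.

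**Conclusion.** The point holds for one descriptive safety variable: time to most severe event for hepatic disorders, dyslipidaemia and myopathy in Section 11.3, and for cardiovascular events in the text of Section 11.4. It repeats the events of time to first onset, does not compare grade between arms, and shifts later when a mild event is followed by a separately recorded worse one.

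Under the assumptions shown, the descriptive median in the escalating arm was later by 4 days (59 against 55, modest escalation) to 36 days (64.1 against 28.1, every active-arm subject with an event escalating). The larger shifts rest on strong escalation in one arm and none in the other, so they are illustrations and not forecasts. The simulated rejection rates are likewise illustrative.

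The safety assessment as a whole is not blind to escalation. What the plan lacks for these groups is a time to a severe event and a maximum-severity count pooled within each AESI. The change is worth making because it is cheap, but no main conclusion of the trial depends on it.

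**What to change.** In Sections 11.3 and 11.4, and in Tables 14.3.1.15.4, 14.3.1.16.4 and 14.3.1.17.4, define the time as onset of the first event of severe grade, less first-dose date, plus 1. Censor every subject without such an event, including those with only milder events, at double-blind completion or early termination. This is in line with the censoring line already written for pruritus in Section 11.3.1. State how events with missing severity are handled; Section 11.2 counts them as severe, but only for its maximum-severity summary.

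Because severe events may be few, also tabulate subject incidence by maximum severity for each pooled AESI group by arm. Keep time to first onset of any grade as it is.

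The cost is a wording change, one re-derived variable and one added table per group, all from severity data already collected. The downside is sparse tables: at low incidence the new time will often rest on very few events, which is why the maximum-severity counts should accompany it.

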### **11.3.1. Pruritus**

Treatment-emergent pruritus, defined as any preferred term that contains “*Prur*,” will be summarized separately by the MedDRA SOC, treatment group, and PT as a subset of all TEAEs.

An analysis of treatment-emergent pruritus event days per subject years on study will be performed. The days at each severity grade, including the total days of event, and the percent of event days on study at each severity grade, including the total, will be summarized.

In order to explore the relationship between pruritus and the investigational product, the following time-to-event analyses will be performed:

- Total duration of treatment-emergent pruritus
  - Duration of each treatment-emergent pruritus event will be calculated as end date – start date +1. For events that are ongoing at Week 16, the Week 16 date will be used as the end date. The sum of each event will be summed for an overall by-patient duration during the DB phase.
- Time to first onset of treatment-emergent pruritus
  - The time to the start of the first episode will be calculated by date of onset of first episode – date of first dose of investigational product + 1.
  - Subjects who never report an AE of pruritus will be censored at the date of completion or discontinuation.
- Time to onset of the most severe treatment-emergent pruritus
  - The time to the start of the most severe pruritus will be calculated by date of onset of the most severe pruritus – date of first dose of investigational product + 1.
  - Subjects who never report a severe AE of pruritus will be censored at the date of study completion or discontinuation.
- Time to resolution of the most severe treatment-emergent pruritus event
  - The time to resolution of the most severe event of treatment-emergent pruritus will be calculated by date of resolution of the most severe event of treatment-emergent pruritus – start date of the most severe event of treatment-emergent pruritus + 1.
  - Subjects whose most severe event of treatment-emergent pruritus is ongoing will be censored at the date of study completion or discontinuation. For subjects that are lost to follow-up, the last contact date will be used.
  - Only subjects that report a pruritus event are included in this analysis.

- For subjects reporting multiple events at the most severe level, the event with the longest duration will be used.
- Separate summaries will be presented for those who discontinue due to pruritus.

The analysis of time-to-event will include the number of subjects with the event (first onset, most severe), the number of subjects without the event (censored), descriptive statistics of total duration of pruritus, descriptive statistics of time for those with an event, and range in days for all subjects. Kaplan-Meier (KM) estimates will be calculated by treatment group. The quartiles, including the median time-to-event and their respective 2-sided 95% CIs, will be presented. KM estimates will be plotted as a “survival curve” for each treatment group, with the number at risk identified. The comparison of OCA to placebo will be summarized using a log-rank test stratified by randomization strata factors.

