## **4. STUDY DESIGN AND PLAN**

This is a Phase 2, double-blind, randomized, placebo-controlled, multicenter study, evaluating the effects of OCA, and the subsequent addition of statin therapy, on lipoprotein metabolism in subjects with NASH with fibrosis stage 1 to 4, but no evidence of hepatic decompensation, in the DB phase, followed by an open-label LTSE phase to evaluate long term safety and efficacy.

Approximately 80 subjects with histological evidence of definite or probable NASH, who meet all inclusion and none of the exclusion criteria will be enrolled in the study. The histological evidence of definite or probable NASH will be based on the central read of a liver biopsy obtained no more than 1 year prior to randomization and a nonalcoholic fatty liver disease activity score (NAS) of 4 or greater. Subjects not using statin therapy (ie, statin-free) and statin-treated subjects may be enrolled. Statin-treated subjects will be required to stop statin treatment (after signing informed consent) for up to 5 weeks, including a 4-week statin washout period, prior to Randomization/Day 1.

Subjects will have a screening period of up to 5 weeks prior to Randomization/Day 1. At the Randomization (Day 1) Visit, subjects will be randomized in a 1:1:1:1 ratio to receive OCA 5 mg, OCA 10 mg, OCA 25 mg, or placebo, orally, once daily, for 16 weeks. Randomization will be stratified by the pre-randomization fasting serum LDLc ( $\leq$ 125 mg/dL or  $>$ 125 mg/dL) and baseline fibrosis stage (stage 1, 2 or stage 3, 4).

[figure not shown]
Subjects will attend on-site clinic visits at Weeks 2, 4, 8, 12, and 16 and will be contacted at Weeks 6, 10 and 14 to assess safety and treatment compliance. At the Week 4 Visit, all subjects will initiate treatment with atorvastatin at a dose of 10 mg once daily. At the Week 8 Visit, atorvastatin will be increased to 20 mg once daily (if 10 mg daily is tolerated), and continued for an additional 4 weeks. After 4 weeks of treatment at 20 mg, the atorvastatin dose may be titrated (up or down) as clinically indicated. The final visit during the DB phase will occur at Week 16, after which subjects may continue into the open-label LTSE.

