## APPENDIX B. HEPATIC DISORDER PREFERRED TERMS AND ASSOCIATED CODES

Preferred Term	Code
5'nucleotidase increased	10000028
Acquired antithrombin III deficiency	10074561
Acquired protein S deficiency	10068370
Acute hepatic failure	10000804
Acute yellow liver atrophy	10070815
Alanine aminotransferase abnormal	10001547
Alanine aminotransferase increased	10001551
Alcoholic liver disease	10001627
Ammonia abnormal	10001942
Ammonia increased	10001946
Anorectal varices	10068924
Anorectal varices haemorrhage	10068925
Antithrombin III decreased	10049547
Ascites	10003445
Aspartate aminotransferase abnormal	10003477
Aspartate aminotransferase increased	10003481
Asterixis	10003547
Bacterascites	10068547
Benign hepatic neoplasm	10004269
Bile output abnormal	10051344
Bile output decreased	10051343
Biliary ascites	10074150
Biliary cirrhosis	10004659
Biliary cirrhosis primary	10004661
Biliary fibrosis	10004664
Bilirubin conjugated abnormal	10067718
Bilirubin conjugated increased	10004685
Bilirubin excretion disorder	10061009
Biopsy liver abnormal	10004792
Blood alkaline phosphatase abnormal	10059571
Blood alkaline phosphatase increased	10059570
Blood bilirubin abnormal	10058477

Preferred Term	Code
Blood bilirubin increased	10005364
Blood bilirubin unconjugated increased	10005370
Blood cholinesterase abnormal	10005429
Blood cholinesterase decreased	10005430
Blood fibrinogen abnormal	10005518
Blood fibrinogen decreased	10005520
Blood thrombin abnormal	10005818
Blood thrombin decreased	10005820
Blood thromboplastin abnormal	10005824
Blood thromboplastin decreased	10005826
Bromosulphphalein test abnormal	10006408
Child-Pugh-Turcotte score abnormal	10077020
Child-Pugh-Turcotte score increased	10068287
Cholaemia	10048611
Cholestasis	10008635
Cholestatic liver injury	10067969
Cholestatic pruritus	10064190
Chronic hepatic failure	10057573
Cirrhosis alcoholic	10009208
Coagulation factor decreased	10009736
Coagulation factor IX level abnormal	10061770
Coagulation factor IX level decreased	10009746
Coagulation factor V level abnormal	10061771
Coagulation factor V level decreased	10009754
Coagulation factor VII level abnormal	10061772
Coagulation factor VII level decreased	10009761
Coagulation factor X level abnormal	10061774
Coagulation factor X level decreased	10009775
Coma hepatic	10010075
Computerised tomogram liver	10076215
Cryptogenic cirrhosis	10063075
Deficiency of bile secretion	10071634
Diabetic hepatopathy	10071265
Drug-induced liver injury	10072268

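### Total pruritus duration is a plain sum over event records with no rule for overlapping or adjoining records, so a day can count twice and the total can exceed the days on study

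*SAP*

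**What the plan says.** SAP Section 11.3.1 sets out the calculation in a few steps.

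- **Which events count.** "Treatment-emergent pruritus, defined as any preferred term that contains" the string Prur. This is a string match, so more than one preferred term can qualify for the same subject.
- **Length of one event.** "Duration of each treatment-emergent pruritus event will be calculated as end date – start date +1". Both the first and the last day are counted.
- **Open events.** "For events that are ongoing at Week 16, the Week 16 date will be used as the end date".
- **Total per subject.** "The sum of each event will be summed for an overall by-patient duration during the DB phase".

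The section expects some subjects to have several events. For time to resolution it provides: "For subjects reporting multiple events at the most severe level, the event with the longest duration will be used". Its closing paragraph then asks for descriptive statistics of the total duration.

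A separate paragraph, placed before the duration rule, asks for days at each severity grade and adds that "the percent of event days on study at each severity grade, including the total, will be summarized". It does not say how those days are counted.

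Section 6.3.3 (Partial Dates) imputes a missing stop day to the end of the month and a fully missing stop date to the end of the subject's double-blind participation. Neither section merges records or limits a calendar day to one count.

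**The concern.** A sum of event lengths equals time with pruritus only if no two records cover the same day. The definition does not guarantee that. Two qualifying terms may run in parallel. One episode may also be split into successive records, for example when the grade changes, with one record ending on the day the next begins. In the first case every shared day counts twice. In the second, the plus 1 on each record counts the handover day twice.

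The result can then be impossible as a duration: more pruritus days than days in the double-blind phase. Pruritus is one of the four adverse events of special interest in Section 11.3, and within that section it is the only one given a duration analysis. Section 5 plans 20 subjects per group, so a single inflated value can move a group's mean or maximum. For example, 60 surplus days in one subject add 60 / 20 = 3 days to a mean taken over the whole group, and more if the mean is taken only over subjects with pruritus.

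**Working it through.** The SAP gives no figure for pruritus duration, so there is none to reproduce. The check applies its rule to assumed event dates and compares the result with the number of distinct calendar days covered.

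**Inputs from the SAP**
- Event length: end − start + 1 (Section 11.3.1).
- Total: sum over events (Section 11.3.1).
- Length of phase: treatment is given "orally, once daily, for 16 weeks" (Section 4), so 16 × 7 = 112 days. If the Week 16 visit falls on Day 113, the phase is 113 days.

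**Assumed inputs:** all event dates below. They are illustrations, not data from the trial.

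**Formulas**
- Rule as written: T = Σ(end − start + 1).
- Unique days: U = number of calendar days covered by at least one event.
- Surplus: T − U. A day covered by k records adds k − 1 surplus days.

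**Results, 112-day phase**

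| Assumed events | T (as written) | U (unique days) | T/112 | U/112 |
|---|---|---|---|---|
| Two concurrent 60-day events | 60 + 60 = 120 | 60 | 107% | 54% |
| Two events, both Days 15–112 | 98 + 98 = 196 | 98 | 175% | 87.5% |
| Days 8–112 and 29–112 | 105 + 84 = 189 | 105 | 168.8% | 93.8% |
| Days 1–30, 30–60, 60–112 | 30 + 31 + 53 = 114 | 112 | 101.8% | 100% |
| Two events, both Days 1–112 | 112 + 112 = 224 | 112 | 200% | 100% |
| Days 10–30 and 50–70 (no overlap) | 21 + 21 = 42 | 42 | 37.5% | 37.5% |

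**When the total exceeds the phase.** Two events with common onset day s, both ongoing at Week 16, give T = 2 × (112 − s + 1). This exceeds 112 when s is 56 or earlier. With a 113-day phase the limit is Day 57, and two events can total at most 226 of 113 days, again 200%.

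**Reading the table.** Concurrent records produce large errors. Shared handover dates produce small ones, one day per handover. Where records do not overlap or share a date, both counts agree, so counting unique days changes nothing for those subjects.

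**The case against.** The strongest reply is that the SAP never says concurrent events are to be added. It defines an event's length and sums events, which is right for episodes that follow one another without a shared date. Whether records overlap depends on how adverse events are entered: by term, by body site, by grade change, or once at maximum severity. Those rules normally sit in the protocol or the case report form instructions, which are not at hand. This stands as a limit on frequency: the SAP does not show that overlap will occur. It does not rescue the rule, which is a complete instruction. A programmer following it would double-count whenever records overlap or share a date.

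A reader might also infer three stronger points that the SAP does not support.

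- **That the percentage of event days is wrong too.** That summary is specified separately and has no stated day count. It is affected only if the programmer borrows the duration sum.
- **That the error favours or penalises one arm.** The SAP gives no pruritus rates, numbers of concurrent terms or grade changes by arm.
- **That the term list shows overlap.** Appendix B includes "Cholestatic pruritus", so a second kind of pruritus term exists. That does not show that any subject would carry it alongside another pruritus term on the same days.

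The consequence is also modest. Section 6.2.8 treats all intervals and p-values as descriptive, Appendix A lists no table solely for total duration, and the planned by-subject pruritus listings could bring overlaps to light. This stands, and it sets the weight of the point.

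**Conclusion.** The rule for total pruritus duration is defective as written, because it can return more pruritus days than the phase contains. The size depends entirely on the assumed records: no error without overlap or shared dates, one day per shared handover date, and up to double the true duration for two fully concurrent events. The percentages rest on a phase of 112 days; using 113 hardly changes them.

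The direct effect is confined to the descriptive summary of total duration. Pruritus incidence, time to first onset and the LDL analyses do not use this sum. It is a minor point, worth settling before database lock because a correction made afterwards would be an unplanned change to a safety summary.

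**What to change.** In Section 11.3.1, replace the summing sentence with a definition of total duration as the number of unique calendar days in the double-blind phase on which the subject has at least one treatment-emergent pruritus event. The existing conventions for ongoing events and partial dates can stay as they are.

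State that the event-days and percentage summary uses the same day count, with each day assigned to one grade, for example the highest recorded that day, so that the grades add up to the total. The highest-grade convention is one option. What matters is that one convention is fixed in advance.

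The cost is about one SAP sentence and a small programming change. No new data are needed, and subjects whose records neither overlap nor share a date keep the same totals.
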